# **Data Monitoring**

- 1. Types of Data
  - Data Accuracy
  - Protocol Compliance
  - Recruitment of Subjects
  - Screen Failures
  - Radiological assessment
  - Safety Monitoring/Management
  - Aspirate quality assays CBC, CD34+, CFU-F

# 2. Responsibilities and Roles for Gathering, Evaluating and Monitoring the Data

- Principal Investigator: [name] (orthopaedics faculty)
  - The principal investigator will be the monitoring entity due to the nature of this study small number of subjects and the study is conducted only at one site
  - Responsible for insuring protocol compliance
  - Responsible for recruiting and consenting patients for study
  - Responsible for collecting and recording all clinical data pre- and post-operatively
  - Responsible for monitoring data collected and evaluating the progress of the study, assessments of data quality, retention, and adverse events
  - Responsible for monitoring safety of research participants from visits with patients
  - Responsible for stopping or modifying protocol if needed
  - Treating surgeon for patients who are enrolled into study
  - Responsible for intraoperative data collection
  - Knowledge of Group assignment

### Research coordinator: [name] CCRC

- Knowledge of Group assignment
- Responsible for monitoring informed consents
- Responsible for reporting all IRB related matters, storing informed consents, and reporting all adverse events to the IRB
- Responsible for recruiting and consenting patients for study
- Responsible intraoperative data collection
- Evaluates protocol compliance with the above investigators to ensure data protection and patient confidentiality
- Responsible for maintaining regulatory documents
- Research Assistant: [name]
  - Responsible for ensuring data collection from patients
  - Responsible for ensuring that x-rays and CT-scan are taken of patients at necessary times
  - Monitors and reports to PI and research coordinator the recruitment and retention status as well as adverse events
  - Ensures protocol compliance
  - Responsible for organizing and storing all patient data in a secure location where only authorized personnel have access
  - Responsible for completing informed consent procedural log

PI: [name]

- Independent Data Safety Monitoring Board: [name], MD & [name]

- Will oversee adverse events and safety of the trial.
- The board will serve as a consult with the principal investigator when identifying and/or grading adverse events
- If the Principal Investigator and one of the Data Safety Monitoring Board members reach a mutual conclusion, the second will not be consulted. If there is a discrepancy between conclusions determined by the Principal Investigator and a Data Safety Monitoring Board member the second board member will be used to make the final determination.
- [name] Assistant Professor & Director of Orthopedic Trauma Research at NYU Hospital for Joint Diseases Department of Orthopedic Surgery has extensive experience particularly in prospective bone marrow asparate studies here at NYU and is an ideal candidate for the DSMB
- [name], Interim Chief of the Division of Spine Surgery, Director Spine Service - Clinical Affairs, Clinical Professor of Orthopedic Surgery, NYU Langone Orthopedic Department NYU School of Medicine is serving the role [name] has held on the DSMB of this study in version prior to April 16th 2018.
- Independent Reviewer / Blinded Clinician / MD to be named:
  - No knowledge of group assignment
  - Performs radiographic analysis post-operatively
  - Assess Outcomes
  - Outcome adjudicator
- Data analyst:
  - No knowledge of group assignment
- 3. Reporting Adverse Events and Unanticipated Problems
  - Adverse event (AE) grading and attributes
    - 1. No adverse event or within normal limits
    - 2. Mild AE, not requiring treatment
    - 3. Moderate AE, resolved with treatment
    - 4. Severe AE, resulting in inability to carry on normal activities and required professional medical attention
    - 5. Life threatening or disabling AE
    - 6. Fatal AE
  - Safety Plan
    - O Adverse events related to study will be detected from follow up visits by the patient and during the post-operative period by the principal investigator and co-investigators, through physical exam assessment and reviewing x-rays and CT scans of the subject. The investigators will try to determine if the adverse event is related to the research itself or an isolated event using the above criteria.
    - The research coordinator, [name], will perform safety reviews (collecting adverse events, reviewing them, and reporting them).
    - o Additionally, upon enrollment and treatment of 10th subject, data safety and monitoring will be conducted by PI to ensure the safety and efficacy of the trial.

- The research assistant will score and review questionnaires to determine if a subject's condition has worsened (adverse event), and if determined by the PI to be related to the surgery, the event will be reported by the research coordinator.
- O All adverse events identified are reported to the PI and the research coordinator Plan for periodic or annual reporting of AEs
  - The IRB will be notified of a serious adverse event and unanticipated adverse event within 24 hours. All other adverse events will be reported annually to the IRB at the time of continuation renewal.
  - All unanticipated adverse events related to the study will be reported to the IRB in an expedited manner if they are Grade 2 and above in severity. Unanticipated patient deaths are reportable within 7 days. The expedited report sent to other organizations can be copied to the GCRC. The investigator will continue to follow or obtain documentation of the resolution course of such an event.

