# Subject Identification, Recruitment and Consent

As part of the standard of care, the subject will have an initial consultation with the PI/MD which includes appropriate physical and radiographic examinations. The subject will be informed of the nature of their spinal disease and treatment options, operative and conservation non operative care. Should the surgeon feel that operative treatment is the best option, they will be eligible for enrollment into this study. Their treatment will not be influenced by the existence of this study.

All study participants will be patients of [name]. The same care will be provided independent of the patient's willingness to be a part of the study. The 60 subjects to be accrued are based on investigator's caseloads. Only patients who are able to understand the English language will be allowed to participate in the study due to the nature of the validated questionnaires that will be given to them.

PI will identify his clinic patient's eligibility for enrollment into the study using inclusion/exclusion criteria. Should the PI/surgeon feel that operative treatment is the best option, subject will be eligible for enrollment into this study. Their treatment will not be influenced by the existence of this study. PI anticipates to enroll up to 4 patients per month, allowing for completion of enrollment in 15 months, but no longer than 2 years.

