#### **5.** Assessments

- Safety reviews will be performed monthly by the monitoring entity (the principal investigator). The monitoring entity will be responsible for determining the relationship of an adverse event and the treatment received. Since the PI sees the subjects regularly for follow up visits, he will be familiar with the subjects' outcomes and patient histories, thereby making it easier to detect AEs if they do arise. This plan allows for prompt detection of unanticipated problems involving risks to subjects.
- Monitor the incidents of pseudarthrosis for both graft groups by PI

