# 7. Communication of Data Safety Monitoring Reports to the IRB

- The IRB will be notified of a serious adverse event and unanticipated adverse event within 24 hours. All other adverse events will be reported annually to the IRB at the time of continuation renewal.
- All unanticipated adverse events related to the study will be reported to the IRB in an expedited manner if they are Grade 2 and above in severity. Unanticipated patient deaths are reportable within 7 days. The expedited report sent to other organizations can be copied to the GCRC. The investigator will continue to follow or obtain documentation of the resolution course of such an event.

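### Adverse-event relatedness has no single referent and no causal criteria, and the condition on reporting questionnaire-detected worsening conflicts with the plan's all-events reporting rules

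*Combined protocol and SAP*

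**What the plan says.** Items below are in the Data Monitoring part of the combined protocol and SAP.

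- **Item 3, Safety Plan, detection:** "Adverse events related to study will be detected from follow up visits by the patient and during the post-operative period".
- **Item 3, judging cause:** "The investigators will try to determine if the adverse event is related to the research itself or an isolated event using the above criteria". The list before it is a severity scale of six levels, from "No adverse event or within normal limits" up to a fatal event. Its title also announces attributes, but no attribution category follows.
- **Item 3, questionnaires:** the research assistant reviews scores for worsening, labelled in the text as an adverse event. Then, "if determined by the PI to be related to the surgery, the event will be reported by the research coordinator".
- **Item 5, Assessments:** the principal investigator, as monitoring entity, is "responsible for determining the relationship of an adverse event and the treatment received".
- **Items 3 and 7, expedited report:** "All unanticipated adverse events related to the study will be reported to the IRB in an expedited manner", provided they are Grade 2 or higher.
- **Items 3 and 7, other IRB reports:** serious and unanticipated events go to the IRB within 24 hours, with no relatedness condition. For the rest, "All other adverse events will be reported annually to the IRB at the time of continuation renewal".
- **Item 2, roles:** the coordinator's duties include sending all adverse events to the IRB. The principal investigator is the treating surgeon, knows the group assignment and is the monitoring entity.

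**The concern.** An event can be related under one of these wordings and unrelated under another. A complication of the fusion operation is related to the surgery, but need not be related to the research or to the graft that was assigned. The investigators have no causal criteria with which to settle it.

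This matters because two reporting routes depend on the answer: the report of questionnaire-detected worsening and the expedited IRB report. The detection sentence also mentions only study-related events, so an undefined filter may act before anything is recorded. The person who attributes questionnaire-detected worsening is unblinded and performed the operation. Safety is a stated purpose of the trial (Purpose of the Study), so the arms should be compared on adverse events that were recorded and reported in the same way.

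**Working it through.** The documents state no figure on this point, so the check is a comparison of texts.

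**1. Referents.** Item 3 uses the study (detection and expedited report), the research (judging cause) and the surgery (questionnaires). Item 5 uses the treatment received. If study and research are taken as one, three distinct referents remain. None is defined.

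**2. Do they differ in this trial?** Research Procedures names the BMAC system, its combination with bone chips and the dosing as specific to the research. Adverse Events/Risks treats BMP use as standard, and Control Fusion describes the control graft as standard of care. On that reading a graft complication is research-related in the BMAC arm and not in the other two. Research Procedures also lists randomization, so one may equally argue that any assigned graft is part of the research. Both readings are open, so related-event labels may not be comparable between arms.

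**3. Criteria for cause.** The only list above the sentence grades severity. A mild event may be caused by the graft, and a fatal one may not be. The scale cannot answer the question put to it.

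**4. Questionnaire route against the general rules.**
- Questionnaire rule: worsening is an adverse event, and it is reported if the principal investigator relates it to the surgery.
- Coordinator's role (item 2): all adverse events go to the IRB.
- Annual rule (items 3 and 7): all remaining adverse events go to the IRB, with no relatedness test.

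For worsening judged unrelated to the surgery, the first rule gives no report and the other two require one.

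**5. Expedited route against the 24-hour rule.** Grade 1 means no adverse event and Grade 2 is mild, so the threshold of Grade 2 excludes no actual event. Among unanticipated events, relatedness to the study is therefore the only working filter in the expedited rule. The 24-hour rule names unanticipated events without that filter. If it covers serious events and unanticipated events as two classes, which I take to be the natural reading, the expedited rule adds a condition to events already due within 24 hours. If it covers only events that are both serious and unanticipated, attribution decides whether a non-serious unanticipated event is expedited or waits for the annual report. The text does not settle which.

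**6. Recording.** The detection sentence speaks of study-related events. Investigation schedule and follow-up has the office assistant record complications that bear on the study, again without a definition.

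**7. Independent check.** Item 2 has the safety board consult on identifying and grading adverse events. It does not mention attribution.

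**8. Counts.** The stopping criteria in item 6 use severity level, mortality, morbidity rate, pseudarthrosis and fusion rate. None tests relatedness. Complications are listed as an outcome without an attribution condition.

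**The case against.** The strongest reply is that little is lost in practice. All identified events go to the principal investigator and the coordinator, and the 24-hour and annual IRB rules carry no relatedness test. The questionnaire sentence says that an event is reported if it is related to the surgery; it does not say only if. The treatment received can fairly be read as the assigned graft, because the protocol elsewhere uses treatment for the study arm.

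Much of this stands. The general rules are broad, and item 5 may already point to the right contrast. Two things survive. If the questionnaire condition restricts nothing, it has no function; if it restricts something, it contradicts the general rules. And a severity scale cannot serve as a test of cause on any reading.

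A reader might go further and infer that attribution changes what is counted, for example in the stopping rules. The documents do not support this, since no count or analysis is limited to related events. A reader might also take the statement "Their treatment will not be influenced by the existence of this study" to mean that no operative complication could ever be research-related. In its place, that sentence follows the surgeon's decision to operate. The graft is randomized, and randomization is listed among the research procedures.

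**Conclusion.** The point holds as a defect in adverse-event recording and reporting. At least three undefined referents are in use, the stated criteria for cause are severity grades, and the questionnaire condition conflicts with the rules that send all adverse events to the IRB. The expedited and 24-hour rules overlap and need reconciling.

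No numerical size can be derived. One might apply the 10-15% complication rate in item 6 to 60 patients and call the resulting events reclassifiable. That rate is given there as a threshold for action, and the documents give no split of complications between operation, graft and research.

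The conclusion rests on reading the questionnaire sentence as a real condition and on treating the study and the research as one referent. It is worth correcting because the change is cheap and takes safety reporting out of the hands of one unblinded judgement.

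**What to change.** 1. In item 3, remove the relatedness condition on questionnaire-detected worsening and from the detection sentence, and align the recording wording in Investigation schedule and follow-up. State that all adverse events are recorded, reported and tabulated by arm, whatever their attribution.
2. Delete the reference to the criteria above. Give causality categories separate from the severity grades.
3. Use one referent throughout items 3, 5 and 7: the assigned graft and its harvest. Relationship to the operation can be recorded separately if wanted.
4. Reconcile the 24-hour and expedited IRB rules, so that it is clear which unanticipated events each covers and whether relatedness plays any part.

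Cost: protocol wording and one field on the adverse-event form.

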### 4. Privacy and Confidentiality

- Case report forms and all other documentation collected by the investigators and research coordinator/assistant will not contain subject names. Each subject will be assigned a subject code. The subject code will consist of 6 characters in an alphanumeric combination. The site will maintain the link between the subject code and the names. Primary data collection will be based on source-documented hospital chart reviews, notes on the source worksheets and subject interviews will be performed by study coordinators/researchers or investigators at each clinical site. Data will be stored in individual subject binders and locked in a secure office and electronically on the secure REDCap system. Only approved research coordinators/investigators will have access to the data.

#### **5.** Assessments

- Safety reviews will be performed monthly by the monitoring entity (the principal investigator). The monitoring entity will be responsible for determining the relationship of an adverse event and the treatment received. Since the PI sees the subjects regularly for follow up visits, he will be familiar with the subjects' outcomes and patient histories, thereby making it easier to detect AEs if they do arise. This plan allows for prompt detection of unanticipated problems involving risks to subjects.
- Monitor the incidents of pseudarthrosis for both graft groups by PI

### **6.** Criteria for Action

- Subject stopping will occur if any adverse events occur that are level 4 or above, or if the subject is unlikely to comply with the follow-up evaluation schedule
- Study stopping will occur if there is a case of mortality. DSMB and IRB review will determine continuation or termination of study.
- Study stopping will occur if there is a greater than normal rate of morbidity as determined by the monitoring entity; the study subject will be un-blinded and the rates of morbidity will be observed for that subject to determine the cause. Acute vs. Subacute vs chronic morbidity complications vary in degree of prevalence, still greater

PI: [name]

than 10-15% complication rate will deviate from the literature anticipated (Hoffmann 2013, Ajiboye 2016). Study stopping will occur if there is a greater prevalence of pseudarthrosis in the BMAC study group; Lumbar pseudarthrosis rates with use of BMP have been estimated to 6.4% in single center studies. (Kim 2013). Similar percentages can be deduced from reported lumbar arthrodesis rates in larger review studies. Use in lumbar fusions showed a 94% arthrodesis average rate for BMP-2, and 85% average arthrodesis rate using bone marrow aspirate (Chun 2015). For these reasons a pseudarthrosis rate of greater than 10-15% would warrant action.

- Study should be stopped if there is a 10% reduction in fusion rates in the studied group relative to the control group which is the current "Gold Standard" of Iliac Crest graft.

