### Intervention

Patients will receive a lumbar fusion with one of the three interbody support grafts listed below:

• INFUSE rhBMP-2 Bone Graft used according to its approved FDA labels, both the original approval performed from an anterior approach using titanium cages as well as the more recent approvals with the use of PEEK cages from a posterior interbody approach. BMP will be placed in a PEEK cage and to be inserted in a posterior or anterior approach;

or

• Allograft infused with adult stem cells from the bone marrow aspirate concentrate harvested from the iliac crest. Harvest® BMAC System delivers high stem cell concentration to the graft site and will be used according to its approved FDA label.

or

- Autograft with bone marrow aspirate (control)
- Enrollment will be 1:1:1
- The study will determine and compare differences in fusion rate and health related quality of life parameters at 6 weeks, 3 months, 6 months, 1 year, and 2 years postoperatively.
- Pre-operative standard care measures include narcotics usage and health-related quality of life measures: Oswestry Disability Index (ODI), Visual Analog Scale (VAS), Euro-Qol 5-dimension (EQ-5D), Health State Scale, PCS, PROMIS Surveys outlined below:
- PROMIS Bank V11 Pain Interference (Adaptive)
- PROMIS Scale v1.0 Pain Intensity 3a(Auto-scoring)
- PROMIS Bank v1.2 Physical Function(Adaptive)
- PROMIS Bank v2.0 Mobility(Adaptive)PROMIS Bank v2.0 Upper Extremity
  \* While PROMIS will be collected, it will be optional in this study due to limitation of getting patients to collect PROMIS at enrolling surgeon's site. Data will be collected from pre-operative standard-care measures for this study
- Intra-operative standard care measures include intra-operative and peri-operative blood loss, length of stay in hospital, bone marrow quality, and complications. Data will be collected from intra-operative and peri-operative standard care measures for this study.
- Post-operative standard care measures include fusion status at 1 year via CT scan, and health-related quality of life measures previously defined via RedCAP, radiological outcomes, and complications. Data will be collected from post-operative standard care measures for this study
- The radiologist will be blinded to the patient's treatment at the time of postoperative outcomes analysis. The patients will not be blinded to their assigned treatment arm.

PI: [name]

- Outcome measures will include:

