# **Costs to the Subject**

All of the tests (i.e. physical evaluation and imaging components) will be performed as part of the standard of care. The patient may want to discuss this with his insurance carrier in advance. The patient will be responsible for any co-payments and/or deductibles for services rendered.

The patient or his/her insurance company will be responsible for paying for the 1-year follow-up CT scan because it is part of standard care. Patients will have the option to refuse CT scan in which case they will be excluded from the primary data analysis but will be part of the secondary analysis.

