# Aim 1: Clinical Study

This study will analyze the clinical and radiographic outcomes in terms of pre-operative measures, intra-operative measures, and post-operative measures followed-up for in the three groups.

Primary Outcome Endpoint: As per the primary outcome measure, fusion status at 1 year will be assessed via CT scan by an independent radiologist. Clinical outcomes will be defined by patient reported and health-related quality of life measures previously defined. Differences from preoperative visit to post-operative time points will be compared between the 3 groups by Student t-tests. Based on preliminary data, improvements are expected in these outcome measures: ODI from 33.42 (SD:6.22) to 26.75 (SD:8.19); SF-12 PCS from 29.00 (SD:6.05) to 31.42 (SD:6.05); SF-12 MCS from 31.42 (SD: 6.50) to 35.75 (SD: 13.82); NRS from 8.17 (SD: 1.27) to 5.93 (SD: 1.90). Multivariate regression analysis, controlling for age, sex, race, and charlson comorbidity index, will be performed to determine the effect of treatment on reaching MCID values, as defined in Parker et al 2012.[2]

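### Stopping subjects at a level 4 or higher adverse event leaves their 1-year CT and later outcomes unsecured, so loss from the trial may depend on outcome

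*Combined protocol and SAP*

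**What the plan says.** All references are to the combined protocol and SAP.

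- **Data Monitoring, item 6 (Criteria for Action):** "Subject stopping will occur if any adverse events occur that are level 4 or above", and the sentence goes on "or if the subject is unlikely to comply with the follow-up evaluation schedule". It carries no relatedness condition and no discretion, and the document nowhere defines the term.
- **Data Monitoring, item 3 (Reporting Adverse Events):** the scale runs from 1 (no event) to 6 (fatal). Level 4 is "Severe AE, resulting in inability to carry on normal activities and required professional medical attention"; level 5 is life-threatening or disabling. Poor questionnaire results can also count: staff check whether a subject's "condition has worsened (adverse event), and if determined by the PI to be related to the surgery, the event will be reported".
- **Items 3 and 7:** for unanticipated study-related events of grade 2 and above, "The investigator will continue to follow or obtain documentation of the resolution course of such an event".
- **Intervention:** "Patients will receive a lumbar fusion with one of the three interbody support grafts listed below". No later study treatment is described.
- **Aim 1:** "fusion status at 1 year will be assessed via CT scan by an independent radiologist". The hypothesis section looks to 24 months.
- **Costs to the Subject:** of patients who refuse the CT, "they will be excluded from the primary data analysis but will be part of the secondary analysis". There is no matching provision for stopped subjects.

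**The concern.** In a drug trial, stopping a subject can mean stopping the drug while follow-up goes on. Here the treatment is one operation, so after surgery there is no study treatment left to stop. Read naturally, the rule takes a patient out of the study because of a severe outcome.

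That patient may then have no 1-year CT result and no later questionnaires in the trial data. Loss of this kind is informative: whether a patient is assessed depends on how the patient fared. It can distort the comparison of fusion at 1 year and of quality of life to 24 months. It can also thin the data behind the pseudarthrosis and fusion criteria in item 6, where non-unions found after stopping may not be counted.

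**Working it through.** **1. What stopping can mean.** The Intervention section gives one operation with one graft. The second trigger in the item 6 sentence is expected failure to attend follow-up, which concerns participation rather than treatment. Together these point to the end of study participation. This is an inference, because the term is undefined.

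**2. What the rest of the text secures.** Items 3 and 7 keep following a patient only for events that are both unanticipated and study-related, and only to document how they resolve. They mention neither the CT nor the outcome visits. Anticipated or unrelated level 4 events are not covered at all. The data analysis plan allows imputation without stating a rule, and no analysis set is defined. Item 6 therefore ends something that items 3 and 7 partly continue, and the document does not say where the line falls.

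**3. Numbers available.** Sample Size Analysis gives 20 per arm and 85% completion: 20 × 0.85 = 17, which reproduces the stated figure. The share of patients with a level 4 or higher event is not given, so assume 5% to 15%. The upper end borrows item 6's 10–15% figure, which is for all complications and so is likely too high for level 4 and above.

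- Stopped per arm: 20 × 0.05 = 1 to 20 × 0.15 = 3.
- Left per arm, if stopping is independent of routine loss: 17 × 0.95 = 16.2 to 17 × 0.85 = 14.5 (rounded).

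**4. Effect on the observed non-union rate.** Let F of n patients be non-unions. If *a* non-unions and *b* fused patients are lost before CT, the observed rate is (F − a)/(n − a − b). Take n = 20 and F = 3, since 20 × 0.15 = 3 matches the 85% average arthrodesis rate that item 6 cites for bone marrow aspirate. Routine loss is set aside.

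| Lost before CT | Observed non-union rate |
|---|---|
| none | 3/20 = 15% |
| 1 non-union | 2/19 = 10.5% |
| 2 non-unions | 1/18 = 5.6% |
| 3 non-unions | 0/17 = 0% |
| 2 fused | 3/18 = 16.7% |

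The rate falls when non-unions make up more of the lost patients than F/n (here 15%), and rises when they make up less. The documents do not say which applies.

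**5. Would keeping the CT be enough?** Not for revised patients. A 1-year CT after revision images the revised construct. If two of the three non-unions are revised and then appear fused, CT shows 1/20 = 5% although 3 of 20 index fusions failed. A rule for counting revisions is needed as well.

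**The case against.** The strongest reply is that the defect is an undefined term. The likely non-compliance clause resembles exclusion criterion 12, a screening rule, so it is imperfect evidence of what stopping means after surgery. The CT and visits are routine care, withdrawal does not alter treatment, and data come largely from chart review, so a stopped patient's CT may exist and be usable. No passage excludes stopped subjects from analysis. The triggering event is itself recorded, and serious events go to the IRB within 24 hours. All of this is fair. It limits how firmly the loss can be asserted, but it does not supply a provision that the CT and questionnaires of a stopped subject are collected and used.

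Three stronger readings are tempting, and the documents do not support them.

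- **The rule can only remove fusion failures and so flatters the worse arm.** Level 4 covers any severe event, including complications in patients who fuse, and losing those moves the rate the other way.
- **The rule pushes the arms towards the hypothesised similarity.** Item 6 cites 94% fusion for BMP-2 and 85% for marrow aspirate. If half of the non-unions and no fused patients were lost, these would read 0.94/0.97 = 96.9% and 0.85/0.925 = 91.9%, and the gap would shrink from 9 to 5 points. That one-sided loss is an assumption.
- **Stopped non-unions vanish from the study-stopping criteria.** Item 5 has the PI monitor pseudarthrosis and review safety monthly. A non-union that led to revision is already known to the PI and could still be counted. Only those that would be found after stopping are at risk.

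**Conclusion.** The point holds as a gap in the design. A mandatory rule, triggered by severe outcomes, most naturally ends participation, and nothing secures the primary endpoint or the 24-month outcomes for the patients it affects. The conclusion rests on that reading of an undefined term.

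The possible effect is material with 20 per arm, since one to three patients move the observed non-union rate by several points (from 15% to between 0% and 16.7% in the illustration). These are not estimates of the bias. The documents give neither the frequency of level 4 or higher events, nor their timing relative to the CT, nor the proportion that are non-unions, so net direction and size remain unknown. Events after the 1-year CT would affect only later outcomes, and for a fatal event the rule changes nothing.

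It should be settled before enrolment or by amendment, because outcomes not collected cannot be reliably recovered afterwards.

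**What to change.** Reconcile item 6 with items 3 and 7, define what subject stopping means, and state the following:

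- A level 4 or higher event, or expected non-compliance, does not by itself end outcome data collection.
- Operated subjects remain in the scheduled visits, adverse event collection and 1-year CT through 24 months unless they withdraw consent.
- The date and reason of any revision are recorded.
- A revision for non-union before the 1-year CT counts as not fused, both in the primary endpoint and in the pseudarthrosis and fusion counts of item 6.

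Clinical care after an event, and any clinical threshold for stopping, stay with the investigators; nothing is proposed on either.

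The cost is a short amendment. The visits and CT are already described as routine care, so the remaining burden is some extra effort to retain sicker patients.
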